The project relies on PPI involvement at all stages. PPI representatives from our core project team ([name]), our project-specific PPI group and charity collaborators (Equally Well at The Centre for Mental Health) will be consulted approximately every four months (more frequently if required) and involved in coproduction activities as research progresses. Complexities in this area, which include the heavy tobacco addiction experienced by many mental health service users, call for an approach that supports maximal service user orientation for the development of a relevant, acceptable and successful intervention. PPI representatives will be involved in the planning of the research, the development of service user-oriented intervention and research materials (e.g. leaflet), aspects of research conduct (e.g. development of topic guides for qualitative interviews in the pilot trial), networking with existing PPI groups nationally, and dissemination activities with a focus on informing national policy in this area.

STUDY FLOW CHART

Patient mental health records will be screened by research fellows prior to visits to CMHT or GP sites for CPA review/physical health screen. On appointment day, MHR or trained CPN will check eligibility and consent participants at community clinic/GP.

Inclusion criteria

[figure not shown]
 Participants who are current smokers, interested in cutting down or quitting; 2. No mental health inpatient stay in last 3 months; 3. Age ≥ 18 years; 4. Proficient in English or Urdu; 5. Capacity to provide consent

Exclusion criteria

 Current use of e-cigarettes;
 Participation in other smoking cessation trial within last 6 months;
 Pregnant or breastfeeding;
 No treatment for comorbid drug or alcohol problems in last 6 months;
 Alzheimer's disease or dementia diagnosis

Consented eligible participants

Baseline assessment (on site): sociodemographic/smoking behaviour characteristics, health behaviours, primary mental health diagnosis (if available), mental health history

^{*}From enrolment or target quit date (whichever is later; participants are given a week's grace period to set their quit date), carried out at community/GP dinks or at participant home; CMHT – Community Mental Health Team; GP – General Practitioner; CPA – Care Programme Approach; MHR – Mental Health Researcher; CPN – Community Psychiatry Nurse

ABREVIATIONS

Abbreviation Expansion

AE Adverse Event

BCT Behaviour Change Technique

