At a scheduled appointment with a clinician, a brief consultation will be conducted with participants to provide necessary instructions for use of the kit. This appointment can be an online if this is usual practice for those on the online pathway. All participants will be encouraged to consider quitting and to set a target quit date within a week. As set quit dates are likely to vary widely and may change over time, all participants will have a two week 'grace period' from enrolment to decide whether they chose to set a target quit date or not. Participants will be asked to start using the e-cigarette when they quit and to seek out local vape shops to obtain further e-liquid, suited to their individual needs and flavour preference. Participants who do not wish to set a target quit date will be encouraged to use the e-cigarette to reduce cigarette consumption as soon as possible.

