Eligible, consented participants will be asked to complete a brief baseline questionnaire, which will be administered via GDPR-compliant online survey tool REDcap (or in person at the same scheduled appointment as consent, which will require the participant to attend their appointment 30 minutes early to meet with the CSO) assessing sociodemographic and smoking behaviour characteristics, with mental health diagnosis and history being obtained from health care records. For those following the online pathway, once a participant has completed and returned the baseline assessment materials, a link will be sent to the participant to inform them of which group they have been randomised to. For those on the paper-based pathway this will be done in person via a sealed envelope (randomisation will have been generated prior to this by computerised block randomisation at the UCL Clinical Trials Unit see 3.4). At this stage, interaction with participants allocated to the control group will stop to allow them to attend their appointment and receive care as usual. Participants allocated to the intervention group will also attend their appointment and receive care as usual but in addition will receive the e-cigarette starter kit, a leaflet and brief explanation (see 3.5.1).

Follow-up of participants at 1 month in phase 1, and at 1 and 6 months in phase 2, will be undertaken by dedicated mental health researchers. Follow-up surveys will be completed via telephone with an option to receive this by post if preferred. In-person follow up at CMHT sites or participants' homes will be required to biochemically validate self-reported abstinence only through carbon monoxide readings (likely to affect approximately 12 participants in phase 1, and 94 participants in phase 2 as per expected abstinence in control and intervention arms in both the feasibility and full trial; see subsections 3.9 and 4.6 of the submitted application). Figure 1 shows a flow diagram of the participant journey through the study. For COVID-19 risk management, social distancing and hygiene measures will be strictly observed and the study team and participants briefed in advance of the follow up visit. Individual mouth pieces for the monitors will be discarded immediately after use and the monitor core piece disinfected. Staff and participants will be provided with PPE – surgical face masks and plastic gloves.

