The acceptability of the intervention and research procedures will be investigated using a short proforma based on the Theoretical Framework of Intervention Acceptability [63], provided to all participants at follow-up. This will be complemented by qualitative interviews conducted with a sample of approximately 18 participants from the intervention and control group (including, wherever possible, those who disengaged during the course of the study). We will gain insights into patients' experience with the intervention and barriers to and facilitators of success, both in terms of the intervention content and the research process. MHR (or CPN) delivering the intervention in each Trust will provide detailed feedback on their experience, and on barriers and facilitators to

delivery, through feedback diaries and interviews; in addition, in-depth qualitative interviews will be conducted with six MHR/CPNs (two from each Trust).

The attrition rate will be measured as the number of participants who fail to complete follow-up at 1 month. In order to ensure a sufficiently robust effect estimate, which can be affected by high attrition rates in intention to treat analyses [64], attrition rates should not exceed 30%, typical for smoking cessation trials in this population [65] (see 3.14). Reasons for withdrawal will be obtained, where possible. In addition, adherence to treatment (e-cigarette use) will be assessed at 1-month follow up.

3.8.2.2 Clinical (smoking-related) outcomes: This is the primary clinical outcome measure for the feasibility trial, assessed at 1-month follow up. Continuous abstinence will be defined as not having smoked in the two weeks prior to follow-up (weeks 5 and 6 from enrolment), verified by a CO reading below 10 ppm, in keeping with the standard measure used in Stop Smoking Services. This measure will be used to determine whether to progress to Phase II and a full trial, based on the confidence interval approach (see 3.9 and 3.14).

3.8.3 Secondary outcome measures:

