3.8.3.1 Feasibility and acceptability outcomes: Fidelity will be assessed by randomly sampling two intervention sessions per site with trained staff, audio-recording them and coding the use of behaviour change techniques (BCTs) delivered during the session to determine the proportion of BCTs used compared to specification in the manual [66]. Characteristics of 'usual care' in different locations will be also noted, recording two interactions of patients with CMHTs or GPs at each site at baseline and using short proforma with control group participants at follow-up. While the nature of the intervention and delivery format means that contamination is unlikely to be a problem, qualitative exploration will be undertaken with 25% of control group patients to investigate in depth reasons for smoking behaviour change and identifying potential (unintentional) links with our intervention. Based on our findings, we will estimate the presence/extent of contamination in the control group, and the need to change the study procedure (e.g. spacing randomisation per site). Further, the feasibility of intervention delivery via CPNs and using both English and Urdu will be assessed by calculating the number of successfully trained CPNs in each Trust, their recruitment rate and fidelity of intervention delivery as well as the proportion of Urdu speakers successfully recruited into the trial. Participant burden of data collection will be asssessed via qualitative interviews conduction online or via telephone with particpants to assess acceptability, which forms part of our list of measures collected in the feasibility study (Phase 1) to determine stop/go decision for the Phase 2 full trial. Should this issue be raised as a barrier to participation, we will seek to prioritise which measures to retain in the full trial.

3.8.3.2 Clinical (smoking-related) outcomes: Self-reported abstinence 2-4 weeks from enrolment or target quit date (whichever is later) will be recorded at 1-month follow-up. The change in cigarette consumption (and reduction in exhaled breath CO reading) from baseline to 1-month follow-up will be calculated in both intervention and control group participants.

3.8.3.3 Clinical (mental health-related) outcomes: At 1-month follow-up, general and mental health functioning will be assessed as per baseline (see 3.8.1.3).

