3.10 Analyses

The results of the feasibility trial (e.g., preliminary effectiveness, feasibility and acceptability) will determine whether a full RCT (Phase II) is viable. The primary outcome, smoking abstinence for weeks 2-4 from enrolment or target quit date (for those who set a date within one week of enrolment), assessed at 1-month follow-up will be descriptively analysed in line with the one-sided confidence interval approach [47]. Consenting rate, recruitment frequency as well as attrition and adherence rate will be calculated to determine feasibility and to decide which recruitment route is most effective. Qualitative data on acceptability will be analysed using Framework analysis, guided by the Theoretical Framework of Intervention Acceptability [63], to determine themes related to barriers and facilitators to intervention acceptability, and with thematic analysis [73] to explore interview data from trial participants and research and CMHT or allied mental health professional staff. We will also conduct a simple cost effectiveness analysis to determine incremental cost-effectiveness ratios for each additional quitter in the intervention compared with control group. Secondary clinical outcome measures will be analysed using generalised linear models (with intervention allocation specified as between-group factor and time as within-group factor) to determine reductions in cigarette consumption and exhaled breath carbon-monoxide readings and changes in mental health measures from baseline to 1-month follow-up. Fidelity will be determined using an established methodology of BCT-coded audio recording of intervention sessions [66]. Finally, for all quantitative analyses (primary and secondary outcome measures), Bayes Factors will be calculated to examine for non-significant results whether the associations indicated evidence of no effect or data being insensitive to detect an effect, and for significant results, the strength of evidence [74].

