4.5 Measures (see 3.8.1 for baseline measures)

4.5.1 Primary outcome measure

The primary outcome measure is self-reported 7-day point prevalence abstinence, assessed 6 months after study enrolment or target quit date (for those who set a target quit date within one week of enrolment) and verified by exhaled breath CO measurement. Participants will be asked whether they have smoked in the past week and only those responding that they have not had a single puff with a CO reading of less than 10 ppm will be counted as successful quitter. This is a standard outcome measure in tobacco research, recommended for research in populations where the intention to quit on a certain date is not given [79]. Smoking abstinence at 6 months is a strong predictor of long-term effects, thus enabling definitive trials to be conducted efficiently within reasonable resource [80, 81].

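### The Phase I abstinence outcome that feeds the stop/go decision has two different time windows, and the rules for starting its clock conflict

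*Protocol*

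**What the plan says.** **Window.** Section 3.8.2.2 introduces the outcome with "This is the primary clinical outcome measure for the feasibility trial, assessed at 1-month follow up" and continues: "Continuous abstinence will be defined as not having smoked in the two weeks prior to follow-up (weeks 5 and 6 from enrolment"). It requires a CO reading below 10 ppm and says the measure will decide progression to Phase II. Section 3.10 describes the primary outcome as "smoking abstinence for weeks 2-4 from enrolment or target quit date (for those who set a date within one week of enrolment"), also assessed at 1-month follow-up. Section 3.8.3.2, among the secondary outcomes, has: "Self-reported abstinence 2-4 weeks from enrolment or target quit date (whichever is later) will be recorded at 1-month follow-up". Section 3.9 refers only to a 1-month continuous abstinence rate.

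**Clock.** Sections 3.10 and 4.5.1 let the target quit date replace enrolment only if it is set within one week. The Phase II primary is "assessed 6 months after study enrolment or target quit date (for those who set a target quit date within one week of enrolment"). The flow chart footnote, 3.8.3.2 and 4.5.2.1 take whichever of the two dates is later.

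**Grace period.** The flow chart footnote says "participants are given a week" to set the date. Section 3.4.1 says "all participants will have a two week" period from enrolment.

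**Where the quit date is prompted.** The prompt is in 3.4.1, which describes the intervention group, in the paragraph on the kit consultation. Under 3.6.3, once allocation is disclosed, "interaction with participants allocated to the control group will stop" so that they can attend their appointment and receive usual care.

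**The concern.** Stop/go criterion (b) in section 3.13 asks for an estimated effect above zero on this outcome. With two windows in the text, an analyst could calculate that effect in two ways and defend either from the protocol. The follow-up scheduler also cannot tell when the 1-month visit is due.

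The second problem is time zero. A target quit date is chosen after randomisation, by participants who know their allocation, at a contact described for one arm. If one arm sets more or later quit dates, its assessments move later than those of the other arm. The comparison then mixes the effect of the kit with a difference in calendar window. That is avoidable in the outcome that informs progression, and again in the Phase II 1-month outcome.

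**Working it through.** **The plan's own figure.** Section 3.9 states that 36 per group excludes an 8% difference if both arms are at 11%. The standard error is √(2 × 0.11 × 0.89 / 36) = 0.0737. The upper one-sided limit at zero effect is 6.2% at 80% confidence, 7.6% at 85%, 9.5% at 90% and 12.1% at 95%. The statement therefore holds for a level up to about 86%; section 3.9 gives no level. The calculation does not depend on which window is used, so the fix leaves the sample size alone.

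**Overlap of the windows.** Day 1 is the first day after enrolment, so weeks 5-6 are days 29-42. I read weeks 2-4 as days 15-28 after the clock starts. Reading it as days 8-28 gives the same overlaps. I take a date set within one week to mean a quit date no later than day 7. With a clock start on day t, the window ends on day 28 + t, and for t from 0 to 14 it shares t days with days 29-42.

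| Clock starts | Section 3.10 window | Days shared with weeks 5-6 |
|---|---|---|
| Enrolment (day 0) | 15-28 | 0 of 14 |
| Quit date day 3 | 18-31 | 3 of 14 |
| Quit date day 7 (latest under 3.10 and 4.5.1) | 22-35 | 7 of 14 |
| Quit date day 14 (latest under the 3.4.1 grace period) | 29-42 | 14 of 14 |

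Section 3.4.1 expects some participants to set no quit date. For them the overlap is zero. A visit about 30 days after enrolment has also not reached most of days 29-42.

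**Conflict between the clock rules.** Take a quit date on day 10. Under the one-week rule in 3.10 the clock stays at enrolment and the window is days 15-28. Under the later-date rule in 3.8.3.2 it is days 25-38. The same person has two windows, with 0 and 10 days in common with weeks 5-6.

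**Sensitivity of the criterion.** With 36 per arm, one participant is 1/36 = 2.8 percentage points. Independent binomials give the following:

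| Rates, control vs intervention | Intervention leads by exactly one | Tie | Intervention leads |
|---|---|---|---|
| 11.4% vs 19.6% (section 3.9) | 10.7% | 8.2% | 79.0% |
| 11% vs 11% (no effect) | 14.1% | 15.1% | 42.4% |

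If the lead is one, reclassifying one intervention abstainer removes it.

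**Phase II 6-month primary.** The clock moves by at most 1 week (4.5.1), or 2 under the 3.4.1 grace period. Assume a straight-line decline between the protocol's 1-month and 6-month rates over 26 − 4.35 = 21.65 weeks. Control: (11.4 − 7.7)/21.65 = 0.17 points per week, or 0.34 for two weeks. Intervention: (19.6 − 14.4)/21.65 = 0.24 per week, or 0.48 for two. The planned difference is 6.7 points.

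**The case against.** The best defence is that the two windows may describe one intention. A two-week grace period followed by four weeks ends at week 6, so weeks 5 and 6 would be the last fortnight of a month counted from the end of the grace period. That is a plausible origin, and it rules out calling the windows mutually exclusive for everyone. It does not reconcile the text: 3.10 limits the shift to one week, and those without a quit date stay on the enrolment clock.

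Four stronger readings are tempting and are not supported.

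- A reader might infer that only the intervention arm is asked for a quit date. Section 3.4.1 literally addresses all participants, and usual care includes advice on quitting. The placement of the text and the end of research contact with controls make an arm difference possible, but do not establish it.
- A reader might infer that the clock always starts at a quit date. Section 3.8.2.2 counts from enrolment, and 6-month continuous abstinence in 4.5.2.1 runs from two weeks after enrolment.
- A reader might infer that, on the online pathway, weeks 2-4 fall before the kit is used. The appointment is described as some weeks ahead when the invitation letter is sent. The gap from enrolment to appointment is not given.
- A reader might take the 10.7% and 14.1% as the chance that the choice of window changes the decision. They show only how fragile a comparison of 36 per arm is. How often the two windows would classify someone differently cannot be derived from the protocol.

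It is also fair that criterion (b) is one of five, within a funder review.

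**Conclusion.** Wrong as written. The Phase I outcome behind criterion (b) has two windows that cannot both be applied, and one of them is listed as both primary and secondary. The grace period and the rule for moving the clock each appear in two conflicting forms. The windows are fully separate when the clock starts at enrolment, half overlapping for a day-7 quit date, and in agreement only at about day 14.

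A difference in assessment timing between arms is a risk, not a demonstrated bias: the protocol does not say whether controls are asked for a quit date, and no direction of bias can be given. The defect is material for the Phase I outcome and the Phase II 1-month outcome. For the 6-month primary it is small, about 0.2 to 0.5 points within an arm under the assumed linear decline. The overlap counts rest on the day numbering and the reading of the one-week limit given above.

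**What to change.** 1. Write one Phase I primary definition: CO-verified abstinence in the 14 days before a follow-up at a fixed interval, with the visit timed so that it contains the window. Use it identically in 3.8.2.2, 3.9 and 3.10.
2. Anchor outcome timing in both arms and both phases to one date that does not depend on allocation, such as enrolment or randomisation. Remove the target quit date from outcome timing in the flow chart footnote, 3.8.3.2, 3.10, 4.5.1 and 4.5.2.1.
3. Reconcile the one-week and two-week statements on setting a quit date.
4. State whether controls are asked for a quit date and, if so, when and by whom.

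The cost is wording in the protocol and any analysis plan, and a change to the follow-up scheduler. The downside is that participants with a late quit date will have slightly less time since quitting when they are assessed.

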3.11 Phase I Milestones

Study 1 of the project will begin on 1st November 2021, running for 12 months. The time between the award decision and month 1 will be used to begin the relevant approval processes (e.g. NHS Research Ethics Committee), to apply for adoption onto the CRN portfolio and recruit research staff. Months 1-2 will be used to complete the study set up (including intervention training, acquisition of intervention materials, and setting up of Advisory/PPI group and trial committees). Recruitment into the feasibility trial and 1-month follow-up will take place between Months 3 and 8, including qualitative interviews. Qualitative analysis will start immediately and quantitative analysis at the end of follow-up in Months 8-10. The final two months will be used to write and submit a report to YCR (months 10-12). During this time, we will also begin to recruit the additional sites across Yorkshire, to follow up on discussions that have already taken place about the willingness of sites to take part in the full RCT, if funded. We will also start the process of amending relevant approvals and seek a funding review from YCR about continuation to a full trial (see 3.14).

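### The Phase I abstinence outcome behind stop/go criterion (b) is given two different windows and anchors (3.8.2.2 and 3.10), and only one of them states a CO rule

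*Protocol*

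**What the plan says.** Section 3.8.2.2 introduces its abstinence measure with "This is the primary clinical outcome measure for the feasibility trial, assessed at 1-month follow up". It then gives the definition: "Continuous abstinence will be defined as not having smoked in the two weeks prior to follow-up (weeks 5 and 6 from enrolment". The same sentence requires confirmation by exhaled CO under 10 ppm. The section also gives the measure its role: "This measure will be used to determine whether to progress to Phase II and a full trial, based on the confidence interval approach".

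Section 3.10 describes the analysed measure differently: "The primary outcome, smoking abstinence for weeks 2-4 from enrolment or target quit date (for those who set a date within one week of enrolment". It applies the one-sided confidence interval approach to that measure and does not mention CO.

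Section 3.8.3.2 lists a secondary outcome: "Self-reported abstinence 2-4 weeks from enrolment or target quit date (whichever is later) will be recorded at 1-month follow-up".

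Section 3.9 speaks only of a 1-month continuous abstinence rate, so it does not say which version is meant. Section 3.13 makes an estimated effect above zero, by the confidence interval approach, criterion (b) of five for progression.

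The time allowed for a quit date also varies. It is one week in the flow-chart footnote and in 3.10. Section 3.4.1 encourages a date within a week but gives two weeks from enrolment to decide whether to set one.

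**The concern.** Two sections each claim to state the one clinical outcome that feeds the stop/go decision, and they differ in window and anchor. The measure that 3.8.2.2 says decides progression has no analysis in 3.10. The measure that 3.10 does analyse carries the window that 3.8.3.2 assigns to a secondary outcome.

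This affects data capture as well as analysis. Under 3.6.3 only participants who report abstinence are seen in person for CO, about 12 people in Phase I. The period asked about, and the week of the contact, decide who receives that visit and when. A wrong choice cannot be repaired after follow-up has closed. At stake is one of the criteria for funding a 740-person trial.

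**Working it through.** **1. The plan's own figure.** Section 3.9 says 36 per group gives a one-sided interval that excludes 8% when both groups have 11% abstinence. No confidence level is stated, so several were tried.

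- Standard error = sqrt(2 × 0.11 × 0.89 / 36) = 0.0737.
- Upper limit = z × 0.0737: 6.2% at 80%, 7.6% at 85%, 9.5% at 90%, 12.1% at 95%.

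The statement reproduces at an assumed one-sided level of 80-85%, and not at 90% or above. It refers to abstinence at 1 month under either definition, so the inconsistency does not show this figure to be wrong.

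**2. The windows, in days from enrolment.** Weeks 5 and 6 in 3.8.2.2 are days 28-42 for everyone. The 3.10 window ends 28 days after its anchor. Its start is taken as the end of week 2; taking the start of week 2 instead leaves the overlaps below unchanged.

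| Anchor for the 3.10 window | 3.10 window | Overlap with days 28-42 |
|---|---|---|
| Enrolment (day 0) | 14-28 | 0 days |
| Quit date at day 7, the latest 3.10 allows | 21-35 | 7 days (week 5) |
| Quit date at day 14, possible under 3.4.1 only | 28-42 | 14 days |

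The first row includes everyone who sets no quit date, which 3.4.1 permits. Under 3.10's own one-week limit its window never reaches week 6.

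**3. The contact.** Section 3.8.2.2 places the assessment at 1 month. One month after enrolment is about day 28, before weeks 5 and 6 begin. One month after a day-7 quit date is about day 35, when week 6 has not been lived through. Only a contact timed from a quit date near day 14 reaches day 42.

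**4. Weight of one participant.** Inputs are from 3.9: 36 per group, 11.4% and 19.6%.

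- Expected abstainers: 36 × 0.114 = 4.1 and 36 × 0.196 = 7.1, in total 11.2. This agrees with the roughly 12 CO validations in 3.6.3.
- Expected gap between arms: 36 × 0.082 = 2.95, about three people.
- One reclassified participant: 1/36 = 2.8 points.

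**5. Illustration of disagreement (assumed rates, not trial data).** Start from 11.4% and 19.6% self-reported abstinent in weeks 2-4. Assume, equally in both arms, that 10-30% of them lapse by weeks 5-6, that 5-20% are not CO-confirmed, and that 1-3% of the others quit late. In 200,000 simulated trials per scenario, one definition gives a difference above zero and the other does not in 12-26%. The share above zero falls from 79% to 75-65%. If CO is applied to both definitions, and lapse and late quitting are halved to allow for a shared week, disagreement is about 6-14%. Many of these cases are ties at zero under one definition: opposite signs occur in about 4-14% and 1-5% respectively.

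**The case against.** The strongest reply is that the two definitions are nearly the same. If follow-up is counted from the later of enrolment and quit date, as the flow-chart footnote does, and the quit date falls at the end of the two-week grace period, weeks 2-4 after quitting are weeks 5-6 after enrolment. This probably explains where weeks 5 and 6 came from. It rules out the stronger claim that the windows never overlap. It does not remove the conflict: 3.8.2.2 applies those weeks from enrolment to all participants, and 3.10 and the flow chart allow only one week.

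A reader might also infer that the analysed primary outcome is unverified, and so is simply the secondary outcome of 3.8.3.2. The text does not support that. Section 3.10 is silent on CO and does not specify self-report; 3.6.3 plans CO validation, and 3.13 counts successful CO collection among the progression items. Only the 2-4 week window is shared, because the anchor wording differs. What stands is that 3.10 does not state the verification rule.

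Nor does the timetable decide between the definitions. Section 3.11 says "Recruitment into the feasibility trial and 1-month follow-up will take place between Months 3 and 8" and names no abstinence window. Four months of recruitment from month 3 ends with month 6, and a six-week contact would finish in mid-month 8. Only if the buffer month is used would six weeks overrun.

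Finally, criterion (b) is one of five, and 3.5 blinds the applicants and statisticians, which limits choosing a definition to suit the result. Both points lower the stakes, but neither tells the team which question to ask participants, or when.

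**Conclusion.** The point holds as an inconsistency of definition. Two sections fix different windows and anchors for the outcome behind criterion (b), only one states a CO rule, and the week of contact does not fit the weeks 5-6 definition when counted from enrolment. The windows are disjoint from enrolment, share week 5 at a day-7 quit date, and coincide only near day 14.

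The size that follows from the protocol alone is 2.8 points per reclassified participant, against an expected gap of about three people between arms. The definition can therefore change whether the estimate exceeds zero. It would be tempting to quote a fixed probability of conflicting decisions. The simulated ranges of 6-14% and 12-26% rest on lapse, late-quit and non-confirmation rates that the protocol does not give, and they show only that the effect is not negligible. No stated sample size is shown to be wrong. The point still needs correcting before data collection, because the outcome governs progression and the data cannot be collected again.

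**What to change.** Before data collection, state the following once and repeat it identically in 3.8.2.2, 3.9 and 3.10:

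- one abstinence window;
- one anchor, either enrolment or the later of enrolment and target quit date;
- one CO rule;
- the week of the follow-up contact, late enough to cover the whole window.

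Reconcile the one-week and two-week grace periods in the flow chart, 3.4.1 and 3.10, since the anchor depends on them. Choosing weeks 2-4 without settling the anchor would leave the same ambiguity.

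A CO-verified weeks 2-4 measure would match the window in 3.10 and the Phase II 1-month outcome in 4.5.2.1. Label any other abstinence measure, including self-report alone, as secondary with no role in criterion (b).

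The cost is a wording change in a few sections. With the weeks 2-4 option it needs no extra participants or visits.
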